13.2 Exclusion Criteria

Subjects are ineligible for study participation if they meet any of the following criteria at the Screening Visit or the Randomization Visit.

1. Subject is from a vulnerable population, as defined by the US CFR Title 45, Part 46, Section 46.111(b) and other local and national regulations, including but not limited to, employees (temporary, part-time, full time, etc) or a family member of the research staff conducting the study, or of the sponsor, or of the clinical research organization, or of the IRB/IEC.
2. Subject is unwilling to receive, or is intolerant of, SC injections.
3. Subject has a history of sensitivity to ACTH preparations (including but not limited to Acthar and Synacthen).
4. Subject has a history of sensitivity to porcine protein products.
5. Subject has severe active lupus nephritis defined as serum creatinine > 2.5 mg/dL or protein creatinine ratio > 1.5 g/g, or subject has required hemodialysis within 3 months prior to the screening visit or is likely to require hemodialysis throughout the study.
6. Subject has active CNS manifestations of lupus (as evidenced by seizures, psychoses, organic brain syndrome, cerebrovascular accident, cerebritis, or CNS vasculitis) within the 3 months prior to the Screening Visit or develops CNS lupus between the Screening Visit and the first dose of study drug
7. Subject has Type 1 or Type 2 diabetes mellitus or is taking hypoglycemic medication (a history of gestational diabetes mellitus is not exclusionary). Subjects must not have glycosylated hemoglobin (HbA1c) > 6.5 at the Screening Visit.
8. Subject has received any steroid injection (intramuscular, intraarticular or intravenous [IV]) within 4 weeks prior to the Screening Visit (use of topical and/or inhaled steroids is not exclusionary).
9. Subject has received oral prednisone > 30 mg per day or equivalent, cyclosporine, or any nonbiologic investigational drug within 3 months prior to the Screening Visit.
10. Subject has received IV immunoglobulin (Ig) or plasmapheresis within 4 months prior to the Screening Visit.

11. Subject has received cyclophosphamide, abatacept, B cell targeted therapy (anti-CD-22 [epratuzumab] or belimumab), B cell depleting therapy (rituximab or other anti-CD20 agent, or anti-CD52 agent [alemtuzumab]), or any biologic investigational agent within 6 months prior to the Screening Visit.
12. Subject has any known contraindication(s) to Acthar ([Mallinckrodt, 2015](#)) including, but not limited to:
 - Any known history of scleroderma, osteoporosis, or ocular herpes simplex. For the purposes of this study, osteoporosis is defined as evidence of vertebral or long bone fracture, or lumbar T-score > 2.0 SD below the mean of the reference population.
 - Any primary adrenocortical insufficiency, or adrenal cortical hyperfunction.
 - Any current congestive heart failure (defined as New York Heart Association Functional Class III to IV).
 - Peptic ulcer (within 24 weeks prior to the Screening Visit).
 - Recent major surgery (within 24 weeks prior to the Screening Visit).
13. Subject has a history of chronic active hepatitis including active or chronic hepatitis B, or acute or chronic hepatitis C. Subjects must have negative Hepatitis B surface antigen (HBsAg) or Hepatitis B core antibody (HBcAb) and negative Hepatitis C virus antibody (HCV) or HCV polymerase chain reaction (PCR) < 25 IU/mL (HCV PCR will be automatically analyzed if HCV is positive) at the Screening Visit.
14. Subject has a history of tuberculosis (TB) infection, any signs/symptoms of TB, or any close contact with an individual with an active TB infection. Subjects must not have a positive or indeterminate interferon gamma release assay (IGRA) for TB at the Screening Visit.
15. Subject has a clinically significant infection requiring administration of IV antibiotics or hospitalization in the 4 weeks prior to the Screening Visit or between the Screening Visit and the first dose of study drug.
16. Subject has known immune compromised status (not related to SLE or therapies for SLE), including but not limited to, individuals who have undergone organ transplantation or who are known to be positive for the human immunodeficiency virus.
17. Subject has any solid tumor malignancy currently diagnosed or undergoing therapy, or has received therapy for any solid tumor malignancy in the 5 years prior to the Screening Visit; with the exception of treated and cured basal cell carcinoma, treated and cured squamous cell carcinoma of the skin, and treated and cured carcinoma in situ of the cervix.

18. Subject has a diagnosis of, is undergoing therapy for, or has received therapy for a hematologic malignancy in the 5 years prior to the Screening Visit.
19. Subject has current or recent (within 24 weeks prior to the Screening Visit) drug or alcohol abuse as defined in Diagnostic and Statistical Manual of Mental Disorders, Fifth Edition, Diagnostic Criteria for Drug and Alcohol Abuse ([American Psychiatric Association, 2013](#)).
20. Subject has any of the following laboratory abnormalities at the Screening Visit:
 - Hemoglobin ≤ 8.0 g/dL.
 - Platelets $\leq 50,000$ cells/ μ L.
 - Absolute neutrophil count (ANC) ≤ 1000 cells/ μ L.
 - Aspartate aminotransferase (AST), alanine aminotransferase (ALT), or total bilirubin > 2 times upper limit of normal (ULN).
21. Subject has any other clinically significant disease, disorder or laboratory abnormality (including those listed on the Prescribing Information [Section 5: Warnings and Precautions](#) [[Mallinckrodt, 2015](#)]) which, in the opinion of the investigator (by its nature or by being inadequately controlled), might put the patient at risk due to participation in the study, or may influence the results of the study or the subject's ability to complete the study.

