
Concomitant Medications and Treatments:
 
Subjects must remain on stable daily dose of prednisone or prednisone equivalent through Week 16 of the study. Taper of corticosteroid is encouraged between Weeks 16 and 24 as clinically indicated.
 
All other background medications for SLE must remain stable throughout the study.
 
No new immunosuppressant therapies or other new treatments for SLE may be initiated during the study.
 
Subjects are not permitted to receive live or live-attenuated vaccines during the study.
 
All medications and nondrug therapies (eg, blood transfusions, oxygen supplementation) taken from 30 days prior to the Screening Visit and throughout the study will be recorded.
	

Study Drug and Treatment Administration:
 
Acthar is a sterile preparation of purified adrenocorticotrophic hormone (ACTH) analogue formulated in a gel for repository administration. Acthar and its matching placebo will be supplied by the sponsor and administered SC as follows in this study:
 
Treatment A: Acthar 1 mL (80 U) administered SC every other day from Week 0 to 4 and 2x/week from Weeks 5 to 24.
 
Treatment B: Placebo 1 mL administered SC every other day from Week 0 to 4 and 2x/week from Weeks 5 to 24.
	

Efficacy Evaluations:
 
The following efficacy assessments will be evaluated: SRI, SLEDAI-2K, BILAG-2004, PGA, Safety of Estrogens in Lupus Erythematosus National Assessment (SELENA) Flare Index (SFI), Cutaneous Lupus Erythematosus Disease Area and Severity Score (CLASI), 28 Joint Count, and prednisone usage after Week 16.
	

Study Title: A Multicenter, Randomized, Double Blind, Placebo Controlled Study to Assess the Efficacy and Safety of Acthar® Gel in Subjects With Persistently Active Systemic Lupus Erythematosus Despite Moderate Dose Corticosteroids	
Protocol Number: MNK14304067	Type: Phase 4 (US)/ Phase 2 (Outside the US)
Condition/Disease:	Systemic Lupus Erythematosus

group as a factor and the baseline value of the corresponding endpoint as a covariate. Mixed model with repeated measurements will be performed as deemed necessary. Secondary and exploratory endpoints that are proportions will be analyzed using Pearson's chi-square test or Fisher's exact tests.
 
[REDACTED]
 
[REDACTED]
 
[REDACTED]
 
[REDACTED]
 
[REDACTED]
 
[REDACTED]
 
[REDACTED]
	

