The primary goal of lupus treatment is to control or halt the inflammatory disease process while minimizing side effects. Treatments that reduce or eliminate disease activity without adding significant toxicity are needed.

Belimumab (Benlysta®), a B lymphocyte stimulator inhibitor, is an SLE targeted therapy approved by the FDA in 2011. It was the first new SLE drug approved in over 50 years. In the BLISS 52 Phase 3 study, approximately 58% of Benlysta patients (10 mg/kg) responded to treatment and 19% were able to decrease prednisone to < 7.5 mg/day (Navarra et al, 2011). This is compared to approximately 44% of placebo patients who responded to treatment and 12% were able to decrease prednisone to < 7.5 mg/day. Despite the recent approval of Benlysta, a significant unmet need remains for treatments that can improve disease activity and decrease dependence on chronic prednisone use.

As described in the Package Insert, ■■■■ Acthar® Gel (repository corticotropin injection, hereafter referred to as Acthar) contains a highly purified adrenocorticotrophic hormone (ACTH) analogue (Mallinckrodt, 2015). It is approved by the FDA for use during an acute exacerbation or as maintenance therapy in selected cases of SLE. ACTH is a member of the family of structurally related peptides known as melanocortin peptides. Melanocortin peptides, which in addition to ACTH include α -, β -, and γ -melanocyte stimulating hormones, are derived from the natural protein pro-opiomelanocortin and exert their physiologic effects by binding to cell surface G-protein coupled receptors known as melanocortin receptors (MCR) (Mountjoy et al, 1992). Five subtypes of MCRs have been identified to date (MC1R-MC5R), each with different tissue distributions, binding affinity characteristics, and physiological roles (Getting, 2006). ACTH binds to all 5 subtypes of MCR (Schioth et al, 1995) and recent experiments demonstrate that Acthar also has agonist activity for all 5 MCRs (Mallinckrodt, Unpublished Data). Stimulation of cortisol by ACTH is mediated by activation of the MC2R expressed on

adrenal cortical cells. However, biologic activity of ACTH may extend beyond stimulation of adrenal corticosteroid production. MC1, 3, 4 and 5R are expressed on multiple leukocytes subpopulations (eg, T & B cells, macrophages), as well as within target organs (eg, skin, kidney, central nervous system [CNS]) relevant to SLE (Catania et al, 2004).

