14.2 Prohibited Concomitant Medications

The following treatments will not be permitted during the study:

- Administration of live or live-attenuated vaccines.
- Oral prednisone (or equivalent) > 30 mg/day.
- Steroid injections (intramuscular, intraarticular, or IV).
- IV Ig or plasmapheresis.
- Cyclosporine.
- Cyclophosphamide.
- Abatacept.
- B cell targeted therapy, anti-CD-22 (epratuzumab) or belimumab.
- B cell depleting therapy (rituximab or other anti-CD20 agent, or anti-CD52 agent [alemtuzumab]).
- Any other new immunosuppressant therapy or any other new treatment for SLE (initiated after the Screening Visit).

- Any investigational drug, device, or procedure administered as part of a research study.

If any prohibited medication is taken during the study, all pertinent information will be recorded in source documents and the electronic case report form (eCRF). The designated study medical monitor (MM) must be informed immediately so the sponsor may determine whether to continue the subject in the study.

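### Marketed Acthar or other ACTH started before Screening, whether ongoing or recently stopped, is not barred by the eligibility or prohibited-medication rules

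*Combined protocol and SAP*

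**What the plan says.** Section 10.1 describes Acthar as an ACTH analogue and gives its regulatory status: "It is approved by the FDA for use during an acute exacerbation or as maintenance therapy in selected cases of SLE". The protocol is labelled Phase 4 in the US, and Section 16.1.1 stratifies randomization by US versus non-US location, so US patients will enrol.

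In Section 13.2, Acthar or ACTH appears in three exclusions, none of which concerns use:

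- No. 3: "Subject has a history of sensitivity to ACTH preparations (including but not limited to Acthar and Synacthen".
- No. 12: "Subject has any known contraindication(s) to Acthar", followed by a list of conditions and recent events such as osteoporosis, adrenal disorders, peptic ulcer and major surgery.
- No. 21: a pointer to the label's warnings, within a criterion about diseases, disorders and laboratory abnormalities.

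The exclusions that do concern prior treatment are nos. 8 to 11. They begin with "Subject has received any steroid injection (intramuscular, intraarticular or intravenous [IV]) within 4 weeks prior to the Screening Visit" and "Subject has received oral prednisone > 30 mg per day or equivalent, cyclosporine, or any nonbiologic investigational drug within 3 months". No. 10 covers IV immunoglobulin and plasmapheresis (4 months). No. 11 covers cyclophosphamide, abatacept and B cell agents, ending "or any biologic investigational agent within 6 months prior to the Screening Visit".

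For treatment during the study, Section 14.2 lists named agents and closes its lupus items with "Any other new immunosuppressant therapy or any other new treatment for SLE (initiated after the Screening Visit". Section 14.1 lists permitted drugs; ACTH is not among them, and the list is not stated to be complete. The synopsis adds: "All other background medications for SLE must remain stable throughout the study".

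**The concern.** The trial is meant to compare Acthar with no Acthar on top of stable background therapy. The protocol sets entry windows of 3 to 6 months for cyclosporine, IV immunoglobulin, belimumab and others, but none for the test drug itself. It recruits steroid-treated patients with persistently active lupus, in a country where the drug is approved for maintenance use in selected cases.

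Three things could follow. A placebo subject could continue prescribed Acthar, which puts the test drug in the control arm. A subject who stopped shortly before Screening could carry residual effect into the Week 0 baseline, from which the 4-point SLEDAI-2K reduction in the SRI is measured (Section 17.2). Subjects who already know that the drug helped or failed them could be enrolled, which changes the population studied.

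**Working it through.** **Step 1: can any written rule catch pre-existing marketed ACTH?** Sections 13.1, 13.2, 14.1 and 14.2 are legible, so the gap is not an effect of redaction.

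| Rule | Reaches | Marketed ACTH started before Screening? |
|---|---|---|
| 13.2 no. 3 | Sensitivity to ACTH | No |
| 13.2 no. 8 | Steroid injections by IM, intraarticular or IV route | No: names neither ACTH nor the SC route used here |
| 13.2 no. 9 | Prednisone above 30 mg/day, cyclosporine, nonbiologic investigational drugs | No |
| 13.2 no. 10 | IV immunoglobulin, plasmapheresis | No |
| 13.2 no. 11 | Named agents, biologic investigational agents | No |
| 13.2 no. 12 | Contraindications to Acthar | No |
| 13.2 no. 21 | Disease, disorder or laboratory abnormality | No: not a medication rule |
| 14.2 catch-all | New lupus treatment started after Screening | No: start date is earlier |
| 14.2 last item | Investigational products given within a research study | No: prescribed product |
| 14.1 | Permitted drugs | Silent |
| Synopsis stability line | Background lupus medication | Does not say whether ACTH counts |

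Two neighbouring cases are covered: ACTH newly started after Screening (14.2 catch-all), and ACTH received as an investigational drug within the windows of exclusions 9 or 11.

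**Step 2: reproduce the plan's power.** Section 21.11 gives n = 80 per arm, 30% versus 55%, level 0.05 and 90% power. Section 21.6 gives a two-sided Pearson chi-square test. With P = (p₁ + p₂)/2, normal approximation and pooled variance under the null:

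z = [ |p₂ − p₁|·√n − 1.96·√(2P(1 − P)) ] / √(p₁(1 − p₁) + p₂(1 − p₂)), and power = Φ(z).

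Putting in 0.30 and 0.55: (2.2361 − 1.96 × 0.6991)/0.6764 = 1.280, so power = 0.900. The stated 90% is reproduced. Exact enumeration of the chi-square test gives 0.894.

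**Step 3: hypothetical dilution.** Let f be the share of placebo subjects on ACTH and r their response rate. The placebo rate becomes 0.30 + f(r − 0.30). Neither f nor r is in the documents. Setting r = 0.55 borrows the planned Acthar rate; r = 0.40 is a lower value chosen to show the range.

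| f | Placebo rate, r = 0.55 | Power | Placebo rate, r = 0.40 | Power |
|---|---|---|---|---|
| 0 | 30.00% | 90.0% | 30.0% | 90.0% |
| 5% | 31.25% | 86.6% | 30.5% | 88.7% |
| 10% | 32.50% | 82.5% | 31.0% | 87.3% |
| 20% | 35.00% | 72.4% | 32.0% | 84.2% |

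Example, f = 10% and r = 0.55: (0.225 × √80 − 1.96 × 0.7016)/0.6833 = 0.933, so power = 0.825. On this formula, 90% power with r = 0.55 would need 90, 101 or 128 per arm at f = 5%, 10% or 20%, against 81 at f = 0.

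**The case against.** The strongest reply is that the rules are silent here, not permissive. Section 14.1 and inclusion criteria 11 and 12 name the background lupus drugs that a subject may take, and ACTH is not among them. A site reading 14.1 beside 14.2 finds no permission for ongoing Acthar and might well refuse such a patient. This stands in part. It rules out saying that the protocol authorizes concurrent Acthar. It does not close the gap, because 14.1 is not stated to be exhaustive and about 60 sites would have to settle the point the same way without a written rule.

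A reader might infer more than the documents support:

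- That nothing restricts ACTH during the trial. Section 14.2 does bar a new start after Screening.
- That the synopsis stability line would oblige a subject to stay on Acthar. It asks for stability of background therapy and grants no permission for unlisted drugs.
- That the power losses above are forecasts. The exposure share is unknown. A response rate of 55% is probably at the high end, since a subject continuing ACTH must still meet the disease-activity criteria at entry and then improve by a further 4 points from that on-drug baseline.
- That carry-over always shrinks the contrast. A subject who stopped recently and is assigned placebo may worsen as the effect wanes, which would act the other way.
- That experienced users would break the blind. The documents give no data on this.

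It is also fair to say that randomization should balance prior exposure between arms on average, that open ACTH on placebo pushes toward no difference and does not create a false benefit, and that Section 14 records prior lupus treatments and concomitant medication. All of this limits the severity. Recording, however, identifies exposed subjects only after they have entered.

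**Conclusion.** The point holds for marketed Acthar or other ACTH that was started before Screening and is either ongoing or recently stopped. The written rules allow such a subject to be randomized, and they leave unclear whether ongoing use may continue. Sections 13.2, 14.1 and 14.2 and the synopsis stability line must be reconciled on this.

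For ongoing use, the expected effect is dilution and loss of power. Under the assumptions in the working, power would be about 87%, 82% or 72% for 5%, 10% or 20% exposure at a 55% response, and about 89%, 87% or 84% at a 40% response. For recently stopped use, the direction is not established. The conclusion about the text rests on no assumption; every power figure other than the reproduced 90% does. Because prevalence is unknown and the bias runs mainly toward no difference, this is something the sponsor should fix, not a flaw that invalidates the design.

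**What to change.** 1. Add to Section 13.2 an exclusion for current or recent use of any non-study ACTH preparation, including commercial Acthar. The sponsor should set and justify the window.
2. Add non-study ACTH, including commercial Acthar, to the prohibited list in Section 14.2, whenever it was started.
3. State in Section 14.1 whether the permitted list is exhaustive for lupus drugs, and word the synopsis stability line so that it applies only to permitted background medication.
4. Use the lupus treatment history already collected under Section 14 to identify earlier ACTH exposure.

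The cost is a few lines in an amendment and perhaps a few US candidates lost or delayed. No new data collection is needed, and the planned sample size and primary test stay as they are.

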13.3 Screen Failure

Subjects will be allowed to repeat any single screening assessment/procedure once, if necessary, if it is within the screening window. The subject will not be considered a screen failure unless the repeat assessment/procedure results do not meet eligibility criteria. The period from starting screening related procedures at the Screening Visit to the Randomization Visit must not exceed 28 days, inclusive of any repeat screening procedures.

Subjects who do not meet all of the eligibility criteria at the Screening or Randomization Visits will be deemed a screen failure and the reason for the screen failure will be documented. A subject who is a screen failure at the Screening or Randomization Visit may be rescreened. The subject must repeat all screening procedures. The period from the start of rescreening related procedures to the first dose of study drug must not exceed 28 days. Subjects may be rescreened only once.

14 PRIOR AND CONCOMITANT MEDICATIONS/TREATMENTS

The start and stop date, dose, unit, frequency, route of administration, and indication for all prior (taken within the 30 days prior to the Screening Visit) and concomitant (taken from the Screening Visit through the Follow-up Visit) medications and nondrug therapies (eg, blood transfusions, oxygen supplementation) received will be recorded.

In addition, all prior treatments for SLE will be recorded with start and stop date, dose, unit, frequency and route of administration.

14.1 Permitted Concomitant Medications

The use of antimalarials and NSAIDs is permitted provided the subject has been on a stable dose for at least 4 weeks prior to the Screening Visit and will remain on that dose throughout the study.

The use of methotrexate, azathioprine and mycophenolate mofetil is permitted provided the subject has been on a stable dose for at least 8 weeks prior to the Screening Visit and will remain on that dose throughout the study.

The use of topical and/or inhaled corticosteroids is allowed during the study.

14.2 Prohibited Concomitant Medications

The following treatments will not be permitted during the study:

- Administration of live or live-attenuated vaccines.
- Oral prednisone (or equivalent) > 30 mg/day.
- Steroid injections (intramuscular, intraarticular, or IV).
- IV Ig or plasmapheresis.
- Cyclosporine.
- Cyclophosphamide.
- Abatacept.
- B cell targeted therapy, anti-CD-22 (epratuzumab) or belimumab.
- B cell depleting therapy (rituximab or other anti-CD20 agent, or anti-CD52 agent [alemtuzumab]).
- Any other new immunosuppressant therapy or any other new treatment for SLE (initiated after the Screening Visit).

- Any investigational drug, device, or procedure administered as part of a research study.

If any prohibited medication is taken during the study, all pertinent information will be recorded in source documents and the electronic case report form (eCRF). The designated study medical monitor (MM) must be informed immediately so the sponsor may determine whether to continue the subject in the study.

15 PROCEDURES

The detailed schedule of study procedures is summarized in the Schedule of Study Events (Table 8-1). What follows is a general outline of required procedures and a suggested order for completion.

